Aim 1: To determine how the availability of menthol e-liquids affects combusted tobacco purchasing in menthol cigarette smokers. *Hypothesis 1: Non-menthol cigarette purchasing will be greatest when only tobacco e-liquids are available, indicating that the availability of menthol e-liquids is important for encouraging menthol cigarette smokers to switch to potentially less harmful products.*

Aim 2: To establish if the availability of mint e-liquids is beneficial to menthol cigarette smokers. *Hypothesis 2: Non-menthol cigarette purchasing will not differ by more than 10% when only menthol e-liquids are available compared to when menthol and mint e-liquids are available, indicating that banning mint e-liquids would not discourage menthol cigarette smokers from switching to potentially less harmful products.*

Exploratory Aim: To evaluate the effect of menthol and mint e-liquid restrictions among black menthol cigarette smokers. The effects of the e-liquid marketplace manipulation will be replicated among black smokers.

METHODS AND MEASURES

Overall Study Design

We propose to conduct a within-subjects, multi-session virtual lab study and validation field assessment to determine how the availability of menthol and mint e-liquids affects product purchasing among menthol cigarette smokers. Adult daily menthol cigarette smokers (N=80) will be recruited for this study. After initial eligibility is assessed, participants will complete six virtual sessions (1 baseline, 4 experimental, and 1 follow-up), with three in-person components, and one field assessment to evaluate their tobacco use.

Design and Setting

Participants will be recruited from Winston-Salem, NC and the surrounding area using advertisements on public transit, community flyers, and social media. In a recent trial conducted in Winston-Salem enrolling daily cigarette smokers using similar recruitment methods (U54DA031659; PI: [name]), over 60% of participants were menthol cigarette smokers and 31% identified as black or African American. In-person lab visits to drop off biosamples and pickup study products will be conducted at the Wake Forest Tobacco Control Center of Excellence located in Biotech Place in the Innovation Quarter.

Subject Selection Criteria

We anticipate recruiting up to 100 participants to achieve 80 completers. Equal numbers of black and white participants will be enrolled.

Inclusion criteria:

1. 21+ years of age

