2. Self-report smoking at least 5 cigarettes per day for the past year
3. Self-report smoking menthol cigarette brands > 80% of the time
4. Breathe carbon monoxide (CO) level > 8 ppm or positive urine NicCheck
5. Willingness to use other tobacco products during the study
6. Speak, comprehend, and read English sufficiently to complete study procedures
7. Have home access to a computer, smart phone, or tablet with a web camera and internet access

Exclusion criteria:

1. Currently seeking treatment to quit smoking
2. Self-reported serious medical or psychiatric condition(s) including cardiovascular and chronic respiratory diseases
3. Body temperature > 100.4 F

4. Cold, flu or COVID-19 symptoms including fever, cough, and runny nose in the past 30 days
5. Currently pregnant, breastfeeding or intending to become pregnant for the duration of the study or unwilling to agree to use adequate protection to avoid pregnancy
6. CO reading > 80 ppm
7. Enrollment stratum (Non-Hispanic, white or Black/African American)

Individuals who report smoking non-menthol flavored cigarettes will be excluded since the purpose of the trial is to understand how menthol and mint e-liquid flavor restrictions affect menthol cigarette smokers. We plan to enroll equal numbers of white and African-American/Black participants so we will exclude individuals once the stratum is full (i.e. 40 enrolled). Those with unstable medical or psychiatric conditions are excluded as these symptoms could affect a participant's ability to complete the study. We will exclude those indicating immediate readiness to stop smoking, as participation in this study may not lead to reductions in smoking. We will exclude pregnant people, those trying to become pregnant and those currently breastfeeding due to the potential harmful effects of tobacco use on developing fetuses and infants. Because participants are required to complete portions of the protocol independently during the virtual lab sessions, they will need to be able to independently read and comprehend the study materials.

Those who report past 30 day cold, flu or COVID-19 symptoms will be temporarily excluded as a safety precaution. They will be able to re-screen once they have been symptom-free for more than 30 days.

Telephone Screening Survey

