Sample Size/Estimation/Analysis

Power calculation

Based on prior ETM studies in which the effects of increasing cigarette price were observed in 22-40 participants, a sample size of 80 will be sufficient for answering Aims 1 and 2 as well as the exploratory racial subgroup analyses. No ETM studies have examined the impact of e-liquid flavor availability on combusted tobacco purchasing, so we do not have a direct effect size estimate for our manipulation. In our pilot study, the marketplace manipulation (menthol little cigars available vs. not) resulted in a small effect size (Cohen's $d = 0.31$), likely because JUUL pods were overwhelmingly preferred. When comparing mean menthol/mint e-liquid purchasing vs mean tobacco e-liquid purchasing, there was a large effect size ($d = 1.2$). Thus, we anticipate that our proposed marketplace manipulation will be associated with at least a medium effect size ($d = 0.5$) for non-menthol cigarette purchasing and a sample size of 80 will be sufficient for detecting differences.

For Aim 1 comparing within-participant impact of menthol e-liquid availability on mg of nicotine purchased, our proposed sample size of 80 will have 80% power to detect differences as small as $d=0.31$ using a paired t-test assuming type I error set to 0.05.

Aim 2 hypothesizes that nicotine purchased will be nearly equivalent when mint e-liquid is available or not. Framing the question as an equivalence test, we set a region of equivalence to be [-0.33, 0.33] standard deviations for the difference in effect with the addition of mint. Employing a paired t-test with type I error set to 0.05, our planned sample size of 80 will have 80% power to reject the null that there is an effect outside of [-0.33, 0.33] in favor of the alternative that the effect lies in [-0.33, 0.33]. In the context of mg of nicotine, this would map to an equivalence region of [-20, 20] mg of nicotine, assuming a standard deviation of 60 mg. In other words, we are sufficiently powered to conclude equivalence between mg of nicotine purchased with and without mint available.

Statistical analysis plan

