Linear mixed-effects models with fixed effects for marketplace condition ('tobacco' vs 'menthol & tobacco' vs 'menthol, mint & tobacco') and order of condition administration, and a random effect for participant (to adjust for correlation induced by repeatedly measuring the same participant) will compare the total amount of non-menthol cigarettes and e-liquids purchased at the highest menthol price (Aims 1 and 2). All products will be converted to mg of nicotine (as listed on their packaging) to standardize purchasing across products, as in previous ETM studies.⁵³⁻⁵⁵ Analyses will be conducted to determine if race moderates product purchasing (Exploratory Aim).

ETM data will be used to generate demand curves for each product using an exponential demand equation. Alpha is the rate of change in demand, Q_0 is peak consumption, C is cost, and k is a constant.

Cross-price elasticity estimates will be calculated as the slope of the regression line (B_1) fit to log-transformed purchasing of each alternative product when offered at fixed prices (C) versus log-transformed menthol cigarette price (P): $\log C = B_0 + B_1 \log P$. Exploratory paired t-tests will compare product purchasing during the pre- and post-field assessment ETM task.

For the qualitative data, we will use grounded theory to develop hypotheses related to the topics of interest. Interviews will be audio-recorded and transcribed verbatim. Audio transcriptions will be reviewed for accuracy and entered into Atlas.ti or another qualitative data management software program. Two research staff members will code the first five interviews to achieve greater than 90% interrater reliability and then every 10th interview to ensure integrity. The research team will analyze the interviews using iterative analyses including qualitative research techniques of open and axial coding; major thematic categories; analytical domains; triangulation of data; comparisons within and between groups; and documenting analytical pathways. Saturation will be achieved when no new themes emerge.

HUMAN SUBJECTS PROTECTION

Recruitment Methods

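### The claim that 80 participants suffice for the racial subgroup analyses is not supported for equivalence among Black smokers (about 32% power) or for race moderation (detectable gap about 0.63 SD)

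*Combined protocol and SAP*

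**What the plan says.** In the Analysis Plan, the Power calculation section claims that "a sample size of 80 will be sufficient for answering Aims 1 and 2 as well as the exploratory racial subgroup analyses". The reason offered opens the same sentence: "Based on prior ETM studies in which the effects of increasing cigarette price were observed in 22-40 participants". The section then concedes that no ETM study has looked at e-liquid flavor availability, and it anticipates an effect of at least d = 0.5.

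Two power statements follow, both for the full 80. For Aim 1 the plan claims "80% power to detect differences as small as $d=0.31$ using a paired t-test assuming type I error set to 0.05". For Aim 2 it claims 80% power to conclude equivalence within ±0.33 SD, which it translates to ±20 mg of nicotine with an SD of 60 mg. No figure is given for a single race or for a comparison between races.

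On subgroup size, Subject Selection Criteria says "Equal numbers of black and white participants will be enrolled", and the text after the exclusion criteria says "we will exclude individuals once the stratum is full (i.e. 40 enrolled".

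On purpose, the Exploratory Aim under Objectives says "The effects of the e-liquid marketplace manipulation will be replicated among black smokers". The Statistical analysis plan says "Analyses will be conducted to determine if race moderates product purchasing (Exploratory Aim". The mixed model described there has terms for condition, order and participant, and none for race. The Exploratory Outcomes list includes five purchasing outcomes by race.

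**The concern.** The cited studies concern the effect of raising cigarette prices. They say nothing about power for an equivalence test or for a race-by-condition comparison, and these are what the exploratory aim would call on. The Aim 2 test needs about 80 people to reach its stated power, so a stratum of half that size cannot be assumed to suffice as well.

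The aim and the analysis also differ. The aim speaks of replicating effects among Black smokers, while the analysis named is a test of whether race moderates purchasing. These are different questions, and the plan does not say what result would count as replication.

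The Objectives make information on Black smokers a stated purpose, so that unintended consequences of a flavor policy can be avoided. A reader who trusts the sufficiency claim could take a non-significant interaction as reassurance, or a failed subgroup equivalence test as a warning. At these sample sizes neither reading would be safe.

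**Working it through.** **Inputs from the documents.** N = 80; 40 per race; Aim 1 paired t-test, alpha 0.05, d = 0.31 (stated as detectable) and d = 0.5 (anticipated); Aim 2 margin ±0.33 SD of the paired difference, alpha 0.05.

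**Assumptions.** Aim 1 is two-sided (sidedness is not stated). Aim 2 is two one-sided tests (TOST) at 0.05 each with a true difference of zero, the most favourable case. The standardised SD is the same in each race. The Aim 2 margin is the one in the Power calculation section.

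**1. Reproduce the plan at n = 80.**
- Aim 1: the test statistic is non-central t with n − 1 df and non-centrality d√n = 0.31 × √80 = 2.77. Power is 78.2% (normal approximation Φ(2.77 − 1.96) = 79.2%). Exactly 80% needs d = 0.317. The stated figure reproduces to within two points.
- Aim 2: equivalence is declared when |mean| + t(0.95, n − 1) × s/√n is below the margin. Integrating over the sample SD gives 80.0% (simulation of 200,000 runs: 80.1%). The normal approximation 2Φ(0.33√80 − 1.645) − 1 = 2Φ(1.307) − 1 gives 80.9%. The stated figure reproduces.

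**2. Same formulas at n = 40.**

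| Test among 40 | Key quantity | Power |
|---|---|---|
| Aim 1, d = 0.31 | 0.31 × √40 = 1.96 | 48.1% |
| Aim 1, d = 0.5 | 0.5 × √40 = 3.16 | 86.9% |
| Aim 2, margin 0.33 | 0.33 × √40 − 1.645 = 0.442 | 31.6% exact, 34.2% normal approximation |
| Aim 2, margin 20/60 = 0.333 | as above | 33.1% exact |

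At n = 40, 80% power needs d = 0.454 for Aim 1, or a margin of 0.471 SD for Aim 2. With the margin kept at 0.33, Aim 2 needs 81 people in the stratum.

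**3. Race moderation, one condition contrast at a time, 40 v 40.** This is a two-sample t-test on paired differences with 78 df and non-centrality g√(40/2) = 4.47g, where g is the between-race gap in SDs of the paired difference. The plan states no expected gap, so these values of g are illustrative:
- g = 0.31: non-centrality 1.39, power 27.8%.
- g = 0.5 (for example, the whole anticipated effect in one race and none in the other): non-centrality 2.24, power 59.8%.
- 80% power needs g = 0.634.

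**4. Precision among 40 Black smokers.** The 95% CI half-width is t(0.975, 39)/√40 = 0.32 SD. The 90% CI, which is the interval matching TOST at 0.05 per side, has half-width t(0.95, 39)/√40 = 0.27 SD. Equivalence within ±0.33 would therefore require an estimate within about 0.33 − 0.27 = 0.06 SD of zero when the sample SD equals the assumed SD.

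**5. Sensitivity to dropout.** Subject Selection Criteria also says "We anticipate recruiting up to 100 participants to achieve 80 completers". If the cap of 40 counts enrolments and 20% drop out, 32 per race remain. Aim 2 power is then 16.3%, and Aim 1 power is 39.7% at d = 0.31 and 78.2% at d = 0.5. The main figures use the more favourable 40.

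**The case against.** The aim is labelled exploratory throughout, and exploratory subgroups are not normally powered. Both stated 80% figures are sound at N = 80, so the two main aims are untouched. The plan already lists by-race outcomes, so it foresees reporting by race. It never says that the ±0.33 SD test will be repeated within race, and it gives no expected race-by-condition gap. A mixed model could also borrow residual variance across races and change the figures slightly.

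Most of this stands and limits the point to one over-stated clause and a thin specification. It does not rescue the clause: an exploratory aim need not be powered, but this plan says the sample is sufficient for it and shows no calculation.

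Three stronger readings are tempting, and the documents do not support them:
- *Aim 1 is underpowered in Black smokers.* The 48% applies at d = 0.31, which is the smallest difference the plan says 80 people can detect and also the effect of a different pilot manipulation (little cigars). At the anticipated d = 0.5 the power is 87%.
- *Replication cannot be shown.* Power of 32% makes equivalence unlikely to be shown, not impossible, and Aim 1 alone would probably replicate at d = 0.5.
- *The plan will report a null interaction as replication, or a failed subgroup test as non-replication.* It states no rule either way. The fair criticism is that the rule is missing.

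**Conclusion.** The concern holds in limited form. The sufficiency claim is unsupported for two of the analyses it covers: equivalence among Black smokers, at about 32% power against 80% in the full sample, and race moderation, where only a gap of about 0.63 SD is detectable with 80% power. For Aim 1 among the 40 the claim holds if the effect is about 0.45 SD or more, which includes the anticipated 0.5, and fails near 0.31.

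The 32% depends on reading replication as a repeat of the Aim 2 equivalence test, a reasonable inference that the plan does not spell out. It is also a best case, since any true difference other than zero lowers it. All figures assume equal standardised SDs in the two races.

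**What to change.** - **Power calculation:** remove or qualify the clause about the racial subgroup analyses, and state the figures for 40 per race: Aim 1 detectable d of 0.45 (48% power at d = 0.31, 87% at d = 0.5), Aim 2 equivalence power of about 32%, and a detectable race-by-condition gap of 0.63 SD. Give the favourable and unfavourable Aim 1 figures together.
- **Statistical analysis plan:** add race and its interaction with condition to the mixed model. Report each condition contrast among Black smokers as an estimate, with a 95% CI (about ±0.32 SD) for Aim 1 and a 90% CI (about ±0.27 SD) set against the margin for Aim 2.
- **Interpretation:** state that a non-significant interaction will not be read as replication, and that a failed subgroup equivalence test will not be read as non-replication.

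The cost is a less favourable stated claim for an exploratory aim. No participants, visits or measurements are added.

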For each marketplace condition, participants will complete 10 iterations of the ETM task in ascending order. The prices for menthol cigarettes on the ETM will be set at: \$0.12, \$0.25, \$0.50, \$1.00, \$2.00, \$4.00, \$8.00, and \$16.00 and \$32.00 per cigarette. During one task iteration, menthol cigarettes will be eliminated from the marketplace to simulate a menthol cigarette ban. The costs for the other products will reflect average prices in NC and will not change during the task. For each task iteration, participants will receive individually-tailored account balances approximately equal to the money they would spend on cigarettes for seven days. They can

purchase as many or few products as their account balance allows. Participants are not required to buy products from the ETM or can buy nicotine gum if they prefer to abstain. If they do not buy products from the ETM and do not use tobacco products during the field assessment (biochemically-verified), then they will receive their ETM account balance at Virtual Visit 6. This payment is delayed to reduce the likelihood that they will use this money to buy their preferred brand menthol cigarettes, thus decreasing the validity of the ETM task.

Participants will be instructed to use only the products purchased from the ETM during the subsequent 7-day period after Virtual Visit 5 and told that we will assess adherence by self-report, product accountability, and biochemical verification. The field assessment validates the ETM task by having participants use the products in the real world, simulating the different regulatory environments. Actual product use enables us to measure their subjective experiences such as withdrawal, craving, or product satisfaction as well as assess changes in carbon monoxide exposure, a biomarker of harm, when using products other than menthol cigarettes. We will conduct between-subjects analyses comparing these secondary outcomes by marketplace condition.

In-Person Lab Visit 2

In-Person Lab Visit 2 will be completed up to 48 hours after completing Virtual Visit 5. Participants will complete the COVID screener within 24 hours of their Lab visit via email or phone. Research staff will wear personal protective equipment during the visit including face masks and gloves. The participants will be required to wear facemasks when interacting with the staff. Temperature checks will be conducted immediately upon arrival using a thermal heat scanner.

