All participants will be emailed a cessation manual and local smoking cessation resources.

Product adherence

To verify self-reported tobacco use, all used and unused products will be collected and counted at In-Person Lab Visit 3. Discrepancies between consumption stated on the TLFB versus consumption based on the products returned will be addressed. Non-adherence (i.e., using products not purchased from the ETM) will be assessed via the TLFB and qualitative interview with the importance of honest self-reporting emphasized. If participants report not using combusted tobacco, then CO readings < 6 ppm will verify their self-report.

Compensation

Participants will be paid \$155 for completing the study. They will earn \$30 for completing Virtual Visit 1, \$15 per visit for completing Virtual Visits 2-6 plus a \$50 bonus for completing the study.

Participants that do not meet enrollment criteria at Virtual 1 will earn \$20 for attending the visit. Participants that start but do not complete the study will receive payments for the virtual visits attended. They will not receive the \$50 completion bonus.

ANALYSIS PLAN

Primary Outcome

Protocol Version 10
5.13.22

- Total amount of non-menthol cigarettes purchased when menthol cigarettes are not available.

Secondary Outcomes

- Total amount of tobacco e-liquid purchased when menthol cigarettes are not available.
- Total amount of menthol e-liquid purchased when menthol cigarettes are not available.
- Total amount of mint e-liquid purchased when menthol cigarettes are not available.
- Total amount of dessert and fruit e-liquid purchased with menthol cigarettes are not available

Exploratory Outcomes

- Mean Perceived Health Risk Scale scores
- Mean Product Evaluation Scale scores
- Mean Minnesota Nicotine Withdrawal Scale scores
- Mean Questionnaire on Smoking Urges scores
- Mean Tobacco Product Interest scores
- Mean Tobacco Policy Questionnaire scores
- Total amount of non-menthol cigarettes purchased when menthol cigarettes are not available by race
- Total amount of tobacco e-liquid purchased when menthol cigarettes are not available by race.
- Total amount of menthol e-liquid purchased when menthol cigarettes are not available by race.
- Total amount of mint e-liquid purchased when menthol cigarettes are not available by race.
- Total amount of dessert/fruit e-liquid purchased when menthol cigarettes are not available by race.
- Themes emerging from the qualitative interviews

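### Aim 2 is stated with a 10% limit but tested and powered on an unlinked limit of ±0.33 SD (±20 mg), and the analysis section carries neither

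*Combined protocol and SAP*

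**What the plan says.** - **Objectives, Hypothesis 2.** The claim is that the amount bought of non-menthol cigarettes "will not differ by more than 10% when only menthol e-liquids are available compared to when menthol and mint e-liquids are available". No denominator, test or alpha is given.
- **Power calculation, Aim 2.** The quantity is nicotine: "Aim 2 hypothesizes that nicotine purchased will be nearly equivalent when mint e-liquid is available or not". The region is ±0.33 "standard deviations for the difference in effect with the addition of mint", with a paired t-test, type I error 0.05, N = 80 and 80% power. In mg, "this would map to an equivalence region of [-20, 20] mg of nicotine, assuming a standard deviation of 60 mg". The 10% is not mentioned and no mean is given.
- **Statistical analysis plan.** Linear mixed models "will compare the total amount of non-menthol cigarettes and e-liquids purchased at the highest menthol price (Aims 1 and 2". Products are converted to mg of nicotine. There is no margin, no confidence-interval or two one-sided test rule, and no reference back to the equivalence test.
- **Primary Outcome.** "Total amount of non-menthol cigarettes purchased when menthol cigarettes are not available".
- **Virtual Visits 2-5.** Nine menthol cigarette prices run up to $32.00 per cigarette. Separately, "During one task iteration, menthol cigarettes will be eliminated from the marketplace to simulate a menthol cigarette ban".

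**The concern.** Aim 2 supports a policy claim: that banning mint e-liquids would not discourage menthol smokers from switching. The margin decides that claim. A limit of 10% of purchasing and a limit of ±20 mg are the same thing only at one value of the mean, which the plan never states. The same data could therefore support Aim 2 under one limit and not the other, and the limit could be chosen after the data are seen.

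The analysis section adds to this. It assigns Aim 2 to a model that compares conditions, without the equivalence rule. Read alone, it would allow a non-significant difference to be reported as support for Aim 2, and that is not evidence of equivalence. It also points to the highest-price iteration, which is a different data point from the one that defines the primary outcome. That last mismatch affects Aim 1 equally.

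**Working it through.** **Inputs.** From the Power calculation: N = 80, margin ±0.33 SD, SD 60 mg, paired test, type I error 0.05. From Hypothesis 2: 10%. Assumed: true difference 0, 5% per one-sided test, 60 mg read as the SD of the within-participant difference, and the mean, which is shown as a range.

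**1. The plan's own figure.** Two one-sided paired tests, normal approximation:

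power = 2Φ(0.33 × √80 − 1.645) − 1 = 2Φ(2.952 − 1.645) − 1 = 0.809.

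The exact version, integrating over the sample SD with 79 df, gives 0.800. The stated 80% is reproduced. At 2.5% per side the exact figure is 0.661, so 5% per side is what was used. In mg, 0.33 × 60 = 19.8, about 20, so the SD and mg margins agree with each other at SD 60.

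**2. Link between the limits.** 20 mg is 10% of a mean of 200 mg, 13% of 150 mg and 20% of 100 mg.

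**3. Power for the 10% limit.** In SD units the margin is 0.10 × mean / SD = 0.10 / r, where r is the SD of the paired difference divided by the mean. The smallest margin with 80% power at N = 80 is 0.330 SD, so 80% needs r ≤ 0.10 / 0.330 = 0.303. With SD 60 mg that is a mean of at least 60 / 0.303 = 198 mg.

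| r (assumed) | Margin in SD units | Power for 10% |
|---|---|---|
| 0.25 | 0.400 | 94% |
| 0.30 | 0.333 | 81% |
| 0.35 | 0.286 | 63% |
| 0.40 | 0.250 | 43% |
| 0.50 | 0.200 | 11% |

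The table treats 10% as a fixed number of mg. Simulated ratio tests (50,000 trials each, SD of the difference 60 mg, within-person correlation 0.3 to 0.7) gave 42-43% at a mean of 150 mg, 80-81% at 200 mg and about 96% at 250 mg. The fixed-mg figures are 43%, 81% and 96%, so the simplification is harmless for power.

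**4. Can the limits disagree on the same data?** With SD 60 mg the 90% CI half-width is t(0.95, 79) × 60 / √80 = 11.2 mg. The means are assumed.

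- Mean 150 mg, observed difference 6 mg: CI −5.2 to 17.2. Inside ±20 mg; outside 10% (±15 mg).
- Mean 300 mg, observed difference 15 mg: CI 3.8 to 26.2. Outside ±20 mg; inside 10% (±30 mg).

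The conflict runs in both directions.

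**5. How a 10% rule should be tested.** One could compare the 90% CI with 10% of the observed mean, but this ignores the error in that mean. In simulation with the true Condition 2 mean at 1.1 times the Condition 3 mean (SD of the difference 60 mg, means 200 and 300 mg, correlation 0.3 to 0.9, 40,000 trials), that rule wrongly declared equivalence in 5.7-6.2% of trials. Two one-sided ratio tests did so in 4.9-5.1%.

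**6. Fixed ±20 mg if the SD is not 60.** 80% power needs an SD of at most 20 / 0.330 = 60.6 mg. At assumed SDs of 70 and 80 mg the margin is 0.286 and 0.250 SD, and power is 63% and 43%. So ±0.33 SD and ±20 mg are themselves one limit only at about SD 60.

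**The case against.** Only the Power calculation states a decision framework, with a null, a region, a test and an alpha. The 10% is hypothesis wording. Asked which margin governs, a reader has one operational candidate. This stands, and it means that a choice of limit after the data are seen is a risk, not something the documents establish. It does not remove the conflict, because Hypothesis 2 still makes a 10% claim that the ±20 mg test does not test.

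The Power calculation also sits directly before the Statistical analysis plan under the same heading, so a cross-reference would go far. That is fair: it would be wrong to infer that the plan has no equivalence test. But the analysis section expressly gives Aims 1 and 2 to a mixed-model comparison, so the method named there does differ.

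Nicotine purchased may simply mean the primary outcome in mg, since products are converted to mg. If so, the quantities align, but 10% is still not tied to 20 mg.

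Finally, the highest-price wording is a separate mismatch. It does not leave the outcome undefined, because the Primary Outcome section defines it. It belongs here only because the Aim 2 rule must name the iteration to which it applies.

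**Conclusion.** The point holds. Hypothesis 2 and the equivalence test use different limits that no passage links. The 80% power is correct for ±0.33 SD but not established for 10%. The analysis section omits the equivalence rule and names a different iteration from the primary outcome.

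A reader might infer that the trial is underpowered for the 10% hypothesis. The documents do not support that: they give no mean, and at a ratio of 0.303 or less the 10% limit has at least 80% power. The power range is sensitivity only. Nor is the stated 80% an arithmetic error.

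The figures assume a true difference of zero and that 60 mg is the SD of the paired difference. That is the natural reading, since the region is expressed in SDs of the difference. If 60 mg were instead the SD in a single condition, power for ±20 mg would depend on the within-person correlation: 34% at 0, 81% at 0.5 and 97% at 0.7 (assumed correlations).

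**What to change.** Before outcome data are examined, use one quantity and one margin in the Objectives, the Power calculation and the Statistical analysis plan. The quantity should be mg of nicotine from non-menthol cigarettes in the iteration where menthol cigarettes are unavailable. For the margin, choose one:

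- **(a) Keep 10%.** Name the Condition 3 (menthol, mint and tobacco) mean as the denominator. Test with two one-sided paired tests at 5% each, of Condition 2 minus 0.9 times Condition 3 and Condition 2 minus 1.1 times Condition 3. Do not compare a CI with 10% of the observed mean. Restate power as a function of the assumed SD/mean ratio; 80% needs about 0.303 or less.
- **(b) Keep a fixed ±20 mg.** Replace the 10% in Hypothesis 2. Declare equivalence only if the 90% CI for Condition 3 minus Condition 2 lies inside ±20 mg, and limit the conclusion to that.

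In the Statistical analysis plan, state or cross-reference the chosen rule for Aim 2. For the primary outcome, replace the highest menthol price with the menthol-unavailable iteration; this also corrects Aim 1.

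The cost is wording and, under (a), one restated power sentence, with no extra participants, visits or data. Under (a), stated power may fall below 80%. Under (b), the conclusion is narrower and no longer speaks to 10%, and 80% power holds only if the SD of the paired difference is about 60.6 mg or less.
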